10.2 Dose Modification

The following dose modification rules will be used with respect to potential toxicity. Toxicity will be assessed according to the NCI Common Terminology Criteria for Adverse Events Version 5.0 (CTCAE v5.0).

Therapy will be immediately discontinued for any grade IV treatment-related toxicity that becomes apparent. The exception to this is for grade 4 neutropenia of $<$ 7 days duration. Study treatment will be reinitiated for any grade treatment-related III toxicity pending the reversal of such toxicity after withholding treatment (i.e. the toxicity resolves to the subject's baseline level). In the event of any adverse effect, appropriate medical treatment will be instituted and study treatment will be discontinued if the above toxicity remains.

PROTOCOL TITLE: Phase 2A Study Evaluating a Chemokine-Modulatory Regimen in Patients with Colorectal Cancer Metastatic to the Liver

Table2. Treatment Related Toxicity Management

Treatment-related AEs	Toxicity grade or conditions (CTCAE5.0)	Action taken for Interferon Alpha-2b	Action taken for Rintatolimod	Action taken for Celecoxib	Additional actions
Chills/Fever	Grade 3	None	None	None	Consider additional acetaminophen dosing, supportive care
Pancreatitis	Grade 3	Hold Decreased future doses by 50%	Hold	Hold	Supportive measures as clinically indicated
AST / ALT elevation or Increased bilirubin	Grade 3	Hold until improved to grade 1; Decrease future doses by 50%	Hold	Hold	Advise evaluation for other possible etiologies; consider imaging
Vomiting	Grade 3	Hold until resolved to grade 1; Decrease future doses by 50%	Hold	Hold	
Neuropathy	Grade 2 or greater	Hold until decreased to patient's baseline; Decrease future doses by 50%	None	None	
Depression or other clinically relevant mood disorder	Grade 3	Permanently discontinue; appropriate supportive care/intervention	None	None	
Neutropenia	Grade 3 or greater	Hold until ANC > 1000; Decrease future doses by 50%	Hold	Hold	
Hemorrhage	Grade 2 or greater	None	None	Permanently discontinue	
Myocardial infarction or other arterial thrombotic event	Grade 2 or greater	None	None	Permanently discontinue	

PROTOCOL TITLE: Phase 2A Study Evaluating a Chemokine-Modulatory Regimen in Patients with Colorectal Cancer Metastatic to the Liver

Treatment-related AEs	Toxicity grade or conditions (CTCAE5.0)	Action taken for Interferon Alpha-2b	Action taken for Rintatolimod	Action taken for Celecoxib	Additional actions

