All other clinically significant AEs ¹	Intolerable Grade 2 or Grade 3	Hold therapy until resolved; reduce future doses by 50%	Hold therapy until resolved; reduce future doses by 50%	Hold therapy until resolved	
	Grade 4	Permanently Discontinue	Permanently Discontinue	Permanently Discontinue	
1. Holding of any therapies here for intolerable grade 2 or grade 3 toxicities will be at the discretion of the investigator based upon the nature of the AE and whether one drug can be clearly implicated or not; in the case that one drug can be clearly implicated, only that drug should be dose reduced in the future; in the case that the causative agent is unclear, it is recommended that interferon and rintatolimod are reduced as directed					

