10.2.2 Interferon Alpha-2b and/or rintatolimod Non-hematologic toxicities

Considered to be possibly, probably, or definitely related to Interferon Alpha-2b and rintatolimod:

- Interferon Alpha-2b :

For grade 3 toxicity:

- 1st episode: dose will be held and restarted at the next study visit at a dose reduction of 50%. The dose can be re-escalated if toxicity is reduced to \leq grade 1 or baseline.
- 2nd episode: Treatment will be discontinued

For grade 4 toxicity (except neutropenia of < 7 days duration):

- Treatment will be discontinued

- Rintatolimod:

For grade 3 toxicity:

- 1st episode: dose will be held and restarted at the next study visit at a dose reduction of 33%. The dose can be re-escalated if toxicity is reduced to \leq grade 1 or baseline
- 2nd episode: dose will be held and (if toxicity is resolved to \leq grade 1 or baseline) restarted at the next study visit at a dose reduction of 33%. The dose cannot be re-escalated

PROTOCOL TITLE: Phase 2A Study Evaluating a Chemokine-Modulatory Regimen in Patients with Colorectal Cancer Metastatic to the Liver

For grade 4 toxicity:

- Treatment will be discontinued

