32.3.2 Formulation and packaging

Rintatolimod is supplied as a liquid solution in glass bottles containing 200 mg (100 mg in case of toxicity) per 80 mL. Rintatolimod is a colorless solution containing 2.5 mg/mL in physiological salts (0.15 M NaCl, 0.01 M phosphate, 0.001 M Mg⁺⁺). The product does not contain preservatives or antioxidants.

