32.3.5 Drug administration

Rintatolimod 200 mg will be administered by intravenous infusion after Interferon Alpha-2b on Days 1-3, 8-10, and 15-17. Additional details on the procedures for receiving, storing and using rintatolimod (Ampligen®) can be found in a separate document entitled “Procedures for Receiving, Storing, and Using Ampligen® (Poly I:Poly C₁₂U) Liquid Solution”.

The initial administration should begin at a slow rate of infusion (approx. 20 cc/hour) and increase to 40cc/hour after 30 minutes. Tubing should be flushed with 30 to 50 mL of normal saline solution upon completion.

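### After a grade 3 non-hematologic toxicity, Section 10.2.2 and Table 2 give different rintatolimod rules (33% versus 50% reduction, or no action), and no text says which governs

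*Combined protocol and SAP*

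**What the plan says.** The planned dose is in Section 32.3.5: "Rintatolimod 200 mg will be administered by intravenous infusion after Interferon Alpha-2b on Days 1-3, 8-10, and 15-17".

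Section 10.2.2 covers non-hematologic toxicities possibly, probably or definitely related to interferon and rintatolimod. At grade 3, for rintatolimod:
- First episode: "dose will be held and restarted at the next study visit at a dose reduction of 33"%. Re-escalation is allowed once the toxicity has fallen to grade 1 or baseline.
- Second episode: "2nd episode: dose will be held and (if toxicity is resolved to \leq grade 1 or baseline) restarted at the next study visit", again with a 33% reduction and without re-escalation.

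Table 2 in Section 10.2 (toxicity management, not the reporting table of the same number in Section 17.2) covers treatment-related adverse events, with one column per drug:
- Catch-all row, intolerable grade 2 or grade 3, rintatolimod cell: "Hold therapy until resolved; reduce future doses by 50"%.
- Footnote 1 to that row leaves holding to the investigator and adds: "in the case that one drug can be clearly implicated, only that drug should be dose reduced in the future". If the cause is unclear, it recommends reducing interferon and rintatolimod as the row directs.
- AST/ALT or bilirubin, grade 3, in the order interferon, rintatolimod, celecoxib: "Hold until improved to grade 1; Decrease future doses by 50% Hold Hold".
- Vomiting, grade 3, same order: "Hold until resolved to grade 1; Decrease future doses by 50% Hold Hold".
- Pancreatitis, grade 3: rintatolimod is likewise only held.
- Chills/fever, neuropathy and depression: the rintatolimod cell reads *None*.

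Section 32.3.2 describes the product as "glass bottles containing 200 mg (100 mg in case of toxicity) per 80 mL" and gives the solution strength as 2.5 mg/mL.

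**The concern.** Dose-modification rules are read at the bedside and in the pharmacy, often from the table alone. Here the table and the text disagree on how far rintatolimod is reduced after the same event, and for some events on whether it is touched at all. Two patients with the same toxicity could be managed differently, both within protocol, depending on which page was consulted.

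The rule may be needed more often than rintatolimod's own record suggests. Section 10.2.2 applies from a possible relationship upward, and footnote 1 recommends reducing rintatolimod as well when the cause is unclear. Section 10.2.3 cites 67% grade 3 toxicity with interferon at the same daily dose, on a longer schedule, and expects that the combination may add to side effects. What is at stake is consistent dosing and patient safety.

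**Working it through.** The plan states no figure to reproduce, so the rules are set side by side and applied to 200 mg.

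**1. Do the scopes overlap?** Section 10.2.2 is triggered by grade 3, non-hematologic, and at least possibly related. Table 2 is triggered by treatment-related. A related grade 3 event without its own row, such as fatigue, meets 10.2.2 and can also meet the catch-all row. No precedence rule is stated. Section 10.2.1 (celecoxib) refers the reader to Table 2, but 10.2.2 does not.

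**2. Event not named in Table 2**
- Section 10.2.2: 200 × (1 − 0.33) = 134 mg, or 134 / 2.5 = 53.6 mL.
- Table 2 catch-all row: 200 × (1 − 0.50) = 100 mg, or 100 / 2.5 = 40 mL.
- Difference: 134 − 100 = 34 mg per dose, and 34 / 200 = 17% of the planned dose.
- Illustration: if the event occurs in week 1 and all six doses of weeks 2 and 3 are given reduced without re-escalation, the totals are 6 × 134 = 804 mg against 6 × 100 = 600 mg.

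For interferon the two places agree on 50%, so the conflict over size is specific to rintatolimod.

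**3. Event named in Table 2**

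| Grade 3 event | Table 2, rintatolimod | Section 10.2.2, if related | Relation |
|---|---|---|---|
| Pancreatitis; AST/ALT or bilirubin; vomiting | Hold, no restart dose | Hold, restart at a 33% reduction | Table silent, compatible |
| Chills/fever; neuropathy; depression | None | Hold, restart at a 33% reduction | Contradictory when attributed to rintatolimod |

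The neutropenia row also only holds rintatolimod. It is hematologic, so it lies outside 10.2.2: it is incomplete, not contradictory.

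**4. Restart timing.** For a first episode, 10.2.2 restarts at the next study visit. The catch-all row waits for resolution, and the opening text of 10.2 waits for return to baseline and mentions no reduction. With dosing on consecutive days, the next visit can be the following day.

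**5. Second episode.** The base of the second 33% is not stated. For a patient still on 134 mg:
- taken from 200 mg: 200 × 0.67 = 134 mg, which is no further reduction;
- taken from the current dose: 134 × 0.67 = 89.8 mg, about 90 mg.

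For a patient re-escalated to 200 mg, the two readings coincide at 134 mg.

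**6. Section 32.3.2.** 100 / 200 = 50%. The amount given there for toxicity matches the 50% rule and not the 33% rule.

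**The case against.** The strongest reply is that little is in conflict. In the direct numerical clash, both rules hold the drug and restart it at a reduced dose, 34 mg apart. The hold cells can be read together with 10.2.2, which also begins with a hold and then supplies the restart dose. Footnote 1 gives the investigator discretion. Section 13.3 reports no evidence of dose-limiting organ toxicity with rintatolimod.

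Much of this stands. The gap is modest, and the hold cells are silent, not contradictory. Footnote 1 does not settle the clash, however: its discretion covers holding and which drug is reduced, while the size of the reduction stays as the row directs. Nor does reading the texts together reconcile 33% with 50%, or *None* with a hold and a reduction.

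A reader might infer more than the documents support:
- **A three-way conflict of 134, 100 or 200 mg for one event.** The named rows and the catch-all row exclude each other, so no single event meets all three. No hold cell states 200 mg on restart; that figure is an inference from silence.
- **A second product strength.** Read literally, 100 mg per 80 mL is 1.25 mg/mL, against the stated 2.5 mg/mL. The parenthesis can equally mean 40 mL of the standard solution. Section 32.3.5 also refers to a separate procedures document that is not available here. It might settle preparation, but nothing shows that it settles the reduction rule.
- **An effect on the primary analysis.** Section 19.2 defines evaluability by having both biopsy measurements, and the paired test in Section 19.3 has no exposure term. Nothing in the documents gives the number of patients who would be reduced or the effect on the estimated change.

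**Conclusion.** The contradiction is real but narrower than a blanket statement that the dose after any grade 3 event is undetermined. It has two parts:
- For a related grade 3 non-hematologic event without its own row, 10.2.2 leads to 134 mg and Table 2 to 100 mg.
- For chills/fever, neuropathy or depression at grade 3 attributed to rintatolimod, 10.2.2 requires a hold and a reduction while Table 2 requires nothing.

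Around these lie the missing restart dose in the hold cells, the differing restart timing, the undefined base of the second 33%, and a pharmacy text that matches only one of the two percentages.

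The figures assume a starting dose of 200 mg and a first reduction. The comparison with the catch-all row assumes that the event counts as clinically significant and, if that word also qualifies grade 3, intolerable. This is an inconsistency in dosing instructions that bears on patient safety. No consequence for power or the primary estimate is shown. Which rule is right is a clinical matter on which this point takes no position.

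**What to change.** Reconcile Section 10.2 (opening text, every rintatolimod cell of Table 2 and footnote 1), Section 10.2.2 and Section 32.3.2 so that each event type has one rintatolimod rule. The amended text should state:
- whether rintatolimod is held, and what must be met before it restarts;
- the size of any reduction and the dose it is taken from, for first and second episodes;
- which text governs if table and narrative are both kept;
- what the 100 mg in Section 32.3.2 refers to.

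The remaining *None* cells for rintatolimod (hemorrhage, arterial thrombotic event) should be checked in the same pass. The clinical team decides the content of each rule.

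The cost is a wording amendment, with any pharmacy instructions updated to match. Sample size, endpoints and analysis are unaffected.

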10.2.3 Toxicity Management

The toxicity of high dose interferon (20million units/m²/d) has been established by Kirkwood et al in a number of trials. Most notable was the E1684 trial [68] where HDI (20 million units/m²/d) was administered daily for 5 days x 4weeks. In that trial (n=143), grade 3 toxicities were 67%, grade 4 toxicities were 9% (mainly constitutional and neurologic), and there were 2 treatment related mortalities (grade 5) due to hepatotoxicity. The proportion of Grade 3 and 4 toxicities in that trial were 48.2% for constitutional toxicities (defined as ‘worst grade of any constitutional toxicity, including fever, chills, flu-like symptoms, fatigue, malaise, and diaphoresis), and 66% for non-constitutional toxicities (23.8% for myelosuppression, 13.9% for hepatotoxicity, 28% for neurological toxicity).

While the combination of HDI and rintatolimod may lead to synergistic additive side effects, we will monitor subject toxicities for unexpected increases in constitutional symptoms, myelosuppression, hepatotoxicity, and neurological toxicity. Moreover, the presence of celecoxib may improve the side effect profile. Rather than a separate phase of the study to characterize safety, we will use continual Bayesian monitoring of SAEs with a stopping rule that permits suspension of the trial by the investigator for review by the Data Safety and Monitoring Committee (DSMC). We will focus on monitoring for grade 3 or greater treatment related hematologic toxicities, and grade 4 or greater treatment related non-hematologic toxicities. A non-informative prior distribution of SAEs will be utilized to develop the safety stopping rules (details in Section 19.4).

- **Gastrointestinal Toxicity:**

- Nausea and/or vomiting should be controlled with adequate antiemetic therapy. Prophylactic antiemetic therapy can be used at the discretion of the investigator/sub-investigator. Subjects are encouraged to take plenty of oral fluids.
- Diarrhea should be managed with appropriate antidiarrheal therapy. Subjects should be encouraged to take plenty of oral fluids. If symptoms do not decrease to grade 1 or less with adequate antidiarrheal therapy, all protocol drugs should be held until resolved to < grade 1.

- **Pain**

- For fever or mild local pain, acetaminophen will be utilized at the discretion of the investigator/sub-investigator or designee.

- **Hypersensitivity Reactions**

Caution: Subjects who had a mild to moderate hypersensitivity reaction have been successfully re-challenged, but careful attention to prophylaxis and bedside monitoring of vital signs is recommended. Hypersensitivity reactions to Interferon Alpha-2b and/or rintatolimod will be managed as follows:

- Mild symptoms (e.g., mild flushing, rash, pruritus): Complete infusion. Supervise at bedside. No treatment required.

PROTOCOL TITLE: Phase 2A Study Evaluating a Chemokine-Modulatory Regimen in Patients with Colorectal Cancer Metastatic to the Liver

- Moderate symptoms (e.g., moderate rash, flushing, mild dyspnea, chest discomfort): Stop infusion. Give intravenous diphenhydramine 25 mg and intravenous dexamethasone 10 mg. Resume infusion after recovery of symptoms at a low rate, then, if no further symptoms, at full dose rate until infusion is complete. If symptoms recur, stop infusion. The subject should receive no additional Interferon Alpha-2b or rintatolimod for that week's three-day treatment, but may be retreated after discussion with the investigator. Record toxicity.
- Severe life threatening symptoms (e.g., hypotension requiring pressor therapy, angioedema, respiratory distress requiring bronchodilation therapy, generalized urticaria): Stop infusion. Give intravenous diphenhydramine and dexamethasone as above. Add epinephrine or bronchodilators if indicated. If wheezing is present, that is not responsive to bronchodilators, epinephrine is recommended. Subject should be removed from further protocol therapy. Report as serious adverse event.

10.3 General Concomitant Medication and Supportive Care

Additional chemo-, immune-, and radiotherapies are not permitted during the active treatment period of this trial. Palliative radiotherapy may be permitted for symptomatic control of pain from bone metastases following discussion with the Principal Investigator, provided that the radiotherapy does not affect target lesions.

10.4 Duration of study treatment

A total of 3 weeks of treatment is planned. A repeat liver biopsy will be performed at Day 24 (\pm 4 days) after completion of protocol therapy and the study biopsy; the patient will then proceed onto the follow-up period.

The participant may stop treatment earlier than planned in the event that the following occurs:

- Disease progression
- Unacceptable toxicity
- Withdrawal from study
- Intercurrent illness that prevents further administration of treatment
- Participant non-compliance with study requirements

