9 DESIGN

9.1 Study Design

The intratumoral efficacy of the combination of Interferon Alpha-2b, rintatolimod, and celecoxib will be evaluated by administering fixed doses of each drug. Subjects will receive 3 weeks of the Chemokine Modulation (CKM) regimen, administered on days 1, 2, 3, 8, 9, 10, 15, 16, and 17 of protocol treatment, according to the safe established dosing levels (see Table 1). During this time, subjects will be monitored continuously for safety, based on Bayesian analysis.

Table 1 Dosing

[figure not shown]
Components of the chemokine modulation regimen		
Interferon Alpha-2b (20 million units/M ²) IV over 20 minutes once a day for 3 consecutive days, repeated weekly over 3 weeks (days 1,2,3,8,9,10,15,16,17).	Rintatolimod (200 mg) IV once a day for 3 consecutive days, repeated weekly over 3 weeks (days 1,2,3,8,9,10,15,16,17). Initial administration should begin at a slow rate of infusion (approximately 20 cc/ hour). Increase rate to 40cc/hour after 30 minutes.	Celecoxib (200 mg, orally, twice a day) for 3 consecutive days, repeated weekly over 3 weeks (days 1,2,3,8,9,10,15,16,17). Doses should be given approximately 12 hours apart.

PROTOCOL TITLE: Phase 2A Study Evaluating a Chemokine-Modulatory Regimen in Patients with Colorectal Cancer Metastatic to the Liver

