9.2 Treatment Phase

A total of three weeks of therapy will be planned. Serial liver biopsies will be obtained, with the first performed prior to initiating therapy and the second performed on Day 20 (\pm 2 days). Following completion of the 3 consecutive weeks of treatment, the study treatment period will conclude. In order to secondarily assess clinical benefit, repeat CT imaging will be assessed at day 46 (\pm 3 days). If a patient completes therapy and a decision is made to pursue a further alternate treatment, the subject will come off study; however, in this circumstance, assessment of the next clinical staging study will be requested for determination of RECIST parameters.

Schema

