10 TREATMENT

10.1 Dosing and Administration

10.1.1 Chemokine modulating regimen

For dosing, refer to Table 1. The chemokine modulating regimen will be administered on an outpatient basis at Roswell Park Cancer Institute over 3 consecutive days, every week x 3 weeks (Days 1, 2, 3, 8, 9, 10, 15, 16, 17) in the following order:

- Pretreatment: 500 mL Normal saline IV over 60 minutes
- Pre-meds: Acetaminophen (Tylenol) 650 mg by mouth x 1 dose; Prochlorperazine (Compazine) 10 mg by mouth x 1 dose – administered 30 minutes (\pm 5 minutes) after starting pre-treatment hydration

PROTOCOL TITLE: Phase 2A Study Evaluating a Chemokine-Modulatory Regimen in Patients with Colorectal Cancer Metastatic to the Liver

- Celecoxib: 200 mg orally, administered along with pre-meds
- Interferon Alpha-2b : (20 million units/M²) IV over 20 minutes
- Rintatolimod: 200 mg IV, initial administration should begin at a slow rate of infusion (approximately 20 cc/ hour) and increase to 40 cc/ hour after 30 minutes. Tubing should be flushed with 30 to 50 mL of normal saline solution upon completion. Administration will be followed by 1 hour of observation and vital signs at 30 and 60 minutes post infusion (\pm 5 minutes)
- Celecoxib: 200 mg orally to be taken by the patient at home approximately 12 hours following the initial dose.

Pretreatment and pre-meds listed above are recommendations and may be modified based upon institutional SOC requirements and at the discretion of the investigator. Treatment is intended for an outpatient setting. However, at the investigator's/physician's discretion, the participant may receive treatment as an inpatient, if deemed necessary.

Each 3 day treatment will be initiated after interval history and physical examination is performed and once the relevant laboratory studies have been confirmed to be within clinically acceptable ranges, specifically: ANC \geq 1000/mm³, total bilirubin \leq 1.5 x ULN or \leq 3 x ULN (for patients with Gilbert's Syndrome), AST and ALT $<$ 3 x ULN (or $<$ 150% of values at baseline). Treatment may be delayed up to 3 weeks to allow for resolution of any intercurrent illness or for logistical reasons. Delays beyond 3 weeks will require discussion with the study PI to review appropriateness of continuing therapy on study.

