11 PROCEDURES INVOLVED

11.1 Description of Procedures

The study-specific assessments are detailed in this section and outlined in Appendix F (Study Calendar). Baseline and/or Screening assessments must be performed within 14 days prior to the first dose of investigational product unless otherwise noted. Any results falling outside of the reference ranges may be repeated at the discretion of the investigator. All on-study visit procedures are allowed **a window of ± 1 day** unless otherwise noted.

Unless otherwise defined in the written protocol text, all procedures/assessments will be conducted in accordance with RPCI Clinical Research Services Standard Operating Procedures.

Informed consent **MUST** be completed prior to receiving any study related procedures.

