11.1.1 Screening (performed between days -14 through day -1 unless otherwise specified)

- Recording of concomitant medications
- Medical and Surgical History
- Complete Physical Exam including height and weight
- Vital Signs
- ECOG Performance Status Assessment
- Hematology
- Chemistry
- CEA Level
- ANA testing
- Serum HCG pregnancy testing (within 7 days of Day 1 in women of child-bearing potential only)
- CT and/or MRI (within 28 days of start of treatment)
- EKG
- Liver Biopsy

11.1.2 Evaluations Performed on day 1 of each treatment week (day 1, 8, 15):

- Recording of concomitant medications
- Recording of Adverse Events
- Targeted Physical Exam including weight
- Vital Signs (temperature, blood pressure, pulse rate and respiratory rate) will be performed pre- treatment and at 30 and 60 minutes post rintatolimod
(± 5 minutes).
- ECOG Performance Status Assessment
- Hematology
- Chemistry
- Chemokine Modulating regimen
- Blood (60cc) for correlative studies on Day 1 and Day 15 only (within 1 hour after end of infusion treatment)

PROTOCOL TITLE: Phase 2A Study Evaluating a Chemokine-Modulatory Regimen in Patients with Colorectal Cancer Metastatic to the Liver

11.1.3 Evaluations Performed on days 2 and 3 of each treatment week(days 2,3, 9, 10, 16, 17):

- Recording of concomitant medications
- Recording of Adverse Events
- Vital Signs (temperature, blood pressure, pulse rate and respiratory rate) will be performed pre-treatment and at 30 and 60 minutes post rintatolimod (\pm 5 minutes).
- Chemokine Modulating regimen
- Blood (60cc) for correlative studies on Day 3 only (within 1 hour after end of infusion treatment)

11.1.4 Evaluations Performed on Day 20 (+/- 2 days):

- Recording of Adverse Events
- Liver Biopsy

11.1.5 End of Treatment Visit on Day 29 (+/- 10 days):

- Recording of concomitant medications
- Recording of Adverse Events
- Targeted Physical Exam including weight
- Vital Signs
- ECOG Performance Status
- Hematology
- Chemistry

NOTE: In the event patient cannot tolerate treatment with all 9 days of treatment, then Blood 60cc for correlative will be collected at time that the patient recovers from toxicities (ideally within 1 week of the last infusion). Liver biopsy will also be collected provided there is not an overriding safety concern for the patient.

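### Section 10.4 conflicts with 9.2, 11.1.4 and Appendix F on when the post-treatment biopsy is taken, and its timing after a delayed or shortened course is not specified

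*Combined protocol and SAP*

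**What the plan says.** **Biopsy day.** Section 10.4 states "A repeat liver biopsy will be performed at Day 24", ± 4 days, and adds that this is after protocol therapy is complete. Section 9.2 has "the second performed on Day 20", ± 2 days. Section 11.1.4 is headed "Evaluations Performed on Day 20 (+/- 2 days") and lists the liver biopsy. Appendix F marks the biopsy in its Day 20 (± 2) column. Section 11.1 says "The study-specific assessments are detailed in this section and outlined in Appendix F (Study Calendar").

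**Dosing days and delays.** In Section 9.1 the regimen is "administered on days 1, 2, 3, 8, 9, 10, 15, 16, and 17 of protocol treatment". Section 10.1.1 adds "Treatment may be delayed up to 3 weeks to allow for resolution of any intercurrent illness or for logistical reasons" and "Delays beyond 3 weeks will require discussion with the study PI to review appropriateness of continuing therapy on study".

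**Early stopping.** The NOTE under 11.1.5 covers patients who cannot tolerate all nine treatment days. Their research blood "will be collected at time that the patient recovers from toxicities (ideally within 1 week of the last infusion"), and a liver biopsy is also collected unless an overriding safety concern prevents it. Section 10.4 lists other reasons for stopping early, including progression, intercurrent illness and non-compliance. For any discontinuation, 12.1 requires the end-of-treatment evaluations; the list in 11.1.5 contains no biopsy.

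**Evaluability.** Section 19.2 treats a patient as unevaluable only if the pre- or post-treatment TIL value is missing.

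**Research blood.** Section 11.2 foresees comparing cytokines and immune cell subsets before and after treatment. Sections 11.1.2 and 11.1.3 place the Day 1, 3 and 15 draws within an hour after the infusion. Appendix F also marks a draw at end of treatment.

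**The concern.** The primary analysis is a paired comparison in 12 evaluable patients, and the second biopsy supplies every post-treatment value. Two windows are in force for it. Delays and early stops can widen the spread of intervals further, and 19.2 pools whatever results. Nothing in 19.3 requires the interval to be shown, so a reader could not tell whether the pairs measure CD8 expression at a comparable time after dosing.

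The interim analysis in 19.3 uses the same pairs. It calculates an intra-class correlation and conditional power to help decide between continuing at the current dose and a dose-escalation scheme. The protocol attributes the variability seen so far to lesion choice and necrosis. Timing is another possible source, and the plan does not record it alongside the result.

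For blood, following the schedule exactly leaves no baseline, and none can be obtained once the first infusion has been given. This affects exploratory work only.

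**Working it through.** **1. The plan's own power figure (19.2).** Inputs: n = 12, shift 0.77 SD, one-sided α = 0.1. For a paired t-test, df = 11 and the noncentrality is 0.77 × √12 = 2.667, which gives power 0.900. A simulated sign-flip permutation test (4,000 runs, normal data) gives 0.89. The stated 90% reproduces and does not depend on the biopsy window.

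**2. The windows.** The last scheduled dose is Day 17 (9.1).

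| Source | Calculation | Biopsy days | Days after Day 17 dose |
|---|---|---|---|
| 9.2, 11.1.4, Appendix F | 20 ± 2 | 18-22 | 1-5 |
| 10.4, read as a study-day number | 24 ± 4 | 20-28 | 3-11 |
| 10.4, read literally as days after completion | 17 + (24 ± 4) | 37-45 | 20-28 |

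On the study-day reading of 10.4:
- Shared days: 20-22, which is 3 of the 11 days spanned (18-28).
- Allowed by 10.4 only: Days 23-28, 6 of its 9 days.
- Allowed by the calendar only: Days 18-19, 2 of its 5 days.

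On the literal reading there is no overlap.

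Section 11.1 gives on-study procedures ± 1 day. If that applies to dosing, the last dose falls on Days 16-18. The intervals become 0-6 days (18 − 18 to 22 − 16) and 2-12 days (20 − 18 to 28 − 16).

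**3. Delay.** One 21-day delay puts the last dose at 17 + 21 = Day 38, counted from first dose. The numbering in 9.1 by day of protocol treatment may mean that a delayed session keeps its Day 15-17 label, so that the biopsy day moves with it. This is not stated.

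**4. Early stop, example.** Suppose the last dose is on Day 10, after 6 of 9 treatment days.
- Biopsy kept at Day 20 ± 2: 18 − 10 = 8 to 22 − 10 = 12 days after the last dose.
- Biopsy kept at Day 24 ± 4: 20 − 10 = 10 to 28 − 10 = 18 days.
- Biopsy sharing the NOTE's blood timing: ideally within 7 days.

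All three are evaluable under 19.2.

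**5. Effect on the primary result.** The documents give no time course of CD8 expression after dosing, so no shift in the mean change, variance or power can be derived.

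**6. Blood.** None of the 13 screening items in 11.1.1 is a research draw. All 3 scheduled on-treatment draws are post-infusion. None of the 7 items listed in 11.1.5 is the end-of-treatment draw that Appendix F marks for everyone; 11.1.5 mentions such a draw only in its NOTE on intolerance.

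**The case against.** **The conflict may be a stray line.** Three of four passages agree, 11.1 points to Section 11 and Appendix F for assessments, the study has one centre, and a biopsy on Day 20 meets both windows on the study-day reading. The sentence in 10.4 is also hard to parse. This makes 10.4 the odd one out, but no text makes the calendar prevail, and a biopsy on any of Days 23-28 complies with one section and breaches three.

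**A reader might infer that early-stopped patients have no rule at all.** The documents do not support that. The 11.1.5 NOTE requires a biopsy, if safe, for patients who cannot tolerate the full course. The gap is narrower: the NOTE gives the biopsy no window of its own and is worded for intolerance only.

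**A reader might infer that a delayed patient would be biopsied before the last dose.** Section 10.4 places the biopsy after therapy is complete, which argues against this. What remains open is how long after.

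**Day counts are not effects.** This is correct. They show how far the rules differ and say nothing about how much the CD8 result would change.

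**Blood is a different specimen and a lower tier.** This is also correct. Section 11.2 says only that such analyses may be done, and 8.3 names no blood endpoint. It stands as a secondary point.

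**Conclusion.** The plan contradicts itself on the timing of its only post-treatment primary-endpoint sample: nominally 3-11 versus 1-5 days after the last scheduled dose, with three days in common. These intervals assume dosing on schedule and that 10.4's Day 24 is a study-day number; the literal reading gives Days 37-45 and no common day. How the biopsy moves after a delay is unstated. After intolerance a biopsy is required without a window, and after other early stops 12.1 does not call for one.

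A reader might conclude that the primary result is biased or the study underpowered. The documents do not support either conclusion: the 90% power is not in dispute, and nothing in them converts timing into an effect on the mean change. The consequence is that pairs at unlike intervals can be pooled without this being visible. That should be corrected. Confidence is high on the window conflict. The missing blood baseline is real but exploratory.

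**What to change.** 1. Reconcile 10.4 with 9.2, 11.1.4 and Appendix F to a single biopsy window. The choice of window is the sponsor's.
2. Express it in days after the last regimen dose actually given, so that one rule covers on-time, delayed (10.1.1) and early-stopped patients. Keep the recovery and safety conditions in the 11.1.5 NOTE, and state whether the rule also covers early stops for reasons other than toxicity.
3. In 19.3, list for each pair the interval from last dose to biopsy and the number of treatment days received, beside the primary result. No new evaluability condition is needed.
4. Separately, take the Day 1 research blood before the first infusion (11.1.2, Appendix F), and make 11.1.5 and Appendix F agree on whether the end-of-treatment draw is for all patients.

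**Cost.** Items 1-3 need amendment wording and one listing, with no added biopsy for patients already due one. The listing can be built from the Medication Administration Record (10.5) and the protocol day on the biopsy label (11.3). Because protocol day is ambiguous after a delay, calendar dates are safer, assuming the biopsy date is on record. Item 4 needs no extra blood, but the sample after the first dose is lost; Days 3 and 15 remain. For patients already treated, the interval can only be listed and a blood baseline cannot be recovered.
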